5.2 Severe Impairment Battery (SIB)

The SIB is designed to assess cognitive abilities in patients with severe AD. The SIB is divided into scorable subscales that cover orientation to time and place, attention, language, praxis, visuospatial ability, construction, memory, orientation to name, and social interaction. Scoring gives credit to nonverbal and partially correct answers, thus decreasing the need for language output. There are 51 items, and it takes approximately 20 minutes to complete. The range of possible scores is 0-100 (Panisset 1994).

Although available in the raw data, the SIB scores will be recalculated. Changes from baseline for recalculated SIB subscale scores and the recalculated total score will be summarized at each scheduled timepoint (Days 6, 12, and 33) (Table 14.2.2).

5.3 Alzheimer's Disease Cooperative Study Group Activities of Daily Living Inventory for Severe Alzheimer's Disease (ADCS-ADL Severe)

The ADCS-ADL-Severe assesses the competence of patients with AD in performing basic activities of daily living. The ADCS-ADL-Severe contains 19 items covering physical and mental functioning and independence in self-care (e.g. dressing, grooming, bathing, eating, walking, and toileting). For each ADL, the informant (e.g., caregiver) is first asked if the patient attempted the activity during the past 4 weeks. If a patient did attempt the ADL, the informant is asked to choose the single most accurate definition of the patient's level of performance. The score ranges from 0 to 54, with higher scores indicating less functional impairment (Galasko 2005).

Although available in the raw data, the ADCS-ADL Severe total score will be recalculated. Changes from baseline for recalculated ADCS-ADL Severe total score will be summarized at the scheduled timepoint (Day 33) (Table 14.2.3).

5.4 Alzheimer's Disease Cooperative Study – Clinical Global Impression of Change Caregiver Input rating (ADCS-CGIC)

The ADCS-CGIC is a systematic method for assessing clinically significant change in a clinical trial as viewed by an independent skilled and experienced clinician. The ADCS-CGIC focuses on clinicians' observations of change in the subject's cognitive, functional, and behavioral performance since the beginning of the trial. It relies on both direct examination of the subject and interview of informants (Ferris 1997, Schneider 1997). Unlike a targeted symptom scale, it takes into account a subject's overall functioning in the cognitive, behavioral and functional activity domains.

The ADCS-CGIC is a single value score based on a 7-point scale using the following values:

1 = Marked Improvement

- 2 = Moderate Improvement
- 3 = Minimal Improvement
- 4 = No Change
- 5 = Minimal Worsening
- 6 = Moderate Worsening
- 7 = Marked Worsening

ADCS-CGIC rating (1-7) will be summarized at each scheduled timepoint (Days 6, 12, and 33) (Table 14.2.4).

5.5 Neuropsychiatric Inventory Questionnaire (NPI or NPI-NH)

The NPI (Cummings 1994) comprises 10 behavioral areas and 2 neurovegetative areas (12 domains): delusions, hallucinations, agitation/aggression, depression/dysphoria, anxiety, elation/euphoria, apathy/indifference, disinhibition, irritability/lability, aberrant motor behavior, sleep and nighttime behavior disorders, and appetite/eating changes. Information is gathered from caregivers familiar with the patient's behavior. To serve as an informant, the caregiver must have at least daily contact with the patient. Initial responses to each domain screening question are "Yes" (present) or "No" (absent). If the response to the domain question is "No," the interviewer goes to the next question. If "Yes," the interviewer proceeds to ask the informant a series of sub questions for that domain. For each behavioral domain, there are 4 scores: frequency, severity, domain total score (frequency x severity), and caregiver distress (NPI)/occupational disruptiveness (NPI-NH). Thus, the NPI evaluates response to therapy and provides symptom severity and distress ratings for each symptom reported, as well as total severity and distress scores reflecting the sum of individual domain scores.

The NPI-NH was derived from the NPI (Cummings 1994) to evaluate the neuropsychiatric manifestations and psychopathology of patients with AD and other dementias who reside in nursing homes, extended care facilities, or other long-term care settings. The NPI-NH is an interview-based scale designed to be administered to an informed professional nursing home caregiver (as opposed to a family or home-based caregiver in the standard NPI) involved in the daily care of the subject. Generally, the NPI-NH is used to evaluate changes in subject behavior that have appeared during a given period (Wood 2000).

Change from baseline for NPI or NPI-NH total severity score and total distress score will be calculated and summarized at each scheduled timepoint (Days 12 and 33) (Table 14.2.5).

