4 STUDY DESIGN AND ENDPOINTS

4.1 DESCRIPTION OF THE STUDY DESIGN

This will be a prospective, randomized, double-blind, placebo-controlled study conducted at up to four (4) sites in the United States.

During the Screening Period, subjects will undergo all Screening assessments including an echocardiogram. During the Baseline Period, subjects and their caregivers will complete a series of cognitive and functional assessments.

Subjects that meet eligibility for inclusion in the trial will be randomized in a 2:1 ratio to GRF6019 (Group 1) or placebo (Group 2). Treatment groups will be stratified by sex. There will be one (1) dosing period during which subjects randomized to GRF6019 will receive GRF6019, while subjects randomized to placebo will receive placebo. The dosing period consists of 5 consecutive days (“pulsed dosing”) of IV infusions of 250 mL of either GRF6019 or placebo.

During the 5-day dosing period, subjects who do not already reside in a long-term care/skilled nursing facility will be admitted to such a facility to facilitate safety evaluation. Safety and tolerability assessments will occur at every visit. Cognitive and functional assessments will be performed at Baseline and periodically at subsequent visits through End of Study/Early Termination. In the event of early termination of a subject who has received at least one dose, the End of Study procedures will be performed unless the subject/subject’s legally authorized representative has withdrawn consent. A comprehensive safety and efficacy assessment of all data *in toto* will be conducted at the end of the study.

The overall duration of the study is approximately 12 months from study initiation (i.e., first subject enrolled) to study completion (i.e., last subject last visit). The recruitment period is expected to be approximately 9 months. The subject participation period is 9 weeks from Screening through End of Study, unless prematurely discontinued.

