7.3.5 FOLLOW-UP VISITS

Follow-up Visit 8 (Day 6 + 3 days)

- Review AEs and concomitant medications.
- Collect the following:
 - Vital signs and subject's weight in kilograms.
 - Blood and urine samples for safety labs (fasting samples preferred).
 - Samples for proteomics/epigenetics/biobanking (fasting samples preferred).
- Perform 12-lead ECG.
- Ensure the subject has had an opportunity to eat a meal or snack prior to administering cognitive and functional assessments.
- Administer cognitive and functional assessments in the following order:

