 1. SIB
 2. ADCS-CGIC

Follow-up Visit 9 (Day 12 ± 3 days)

- Review AEs and concomitant medications.
- Collect the following:
 - Vital signs and subject's weight in kilograms.
 - Blood samples for safety labs (fasting samples preferred).
- Ensure the subject has had an opportunity to eat a meal or snack prior to administering cognitive and functional assessments.
- Administer cognitive and functional assessments in the following order:

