15 SCHEDULE OF EVENTS

15.1 SCHEDULE OF EVENTS TABLE

	Screening ^a / Baseline Visit		Treatment					Follow-up		End of Study/ Early Termination Visit
	1	2	3	4	5	6	7	8	9	
Visit	1	2	3	4	5	6	7	8	9	10
Infusion Number			1	2	3	4	5			
Day	Day -28 to -8	Day -7 to -1	1	2	3	4	5	6 + 1-3 days ^b	12 ± 3 days	33 ± 7 days
Week							1		2	5
Informed Consent	X									
Medical History	X									
Demographics	X									
Vital Signs (BP, HR, temp, RR)	X	X	X ¹	X	X	X				
12-lead ECG	X		X ¹		X ¹			X		X
MHIS	X									
Echocardiogram	X									
Physical Exam	X									X
Height	X									
Weight	X		X ¹	X	X	X				
Targeted Physical Exam			X ¹		X ¹		X ¹			
Concomitant Medication	X	X	X ¹	X	X	X				
Adverse Event Review	X ^a	X	X ¹	X	X	X				
Drug Administration										
Randomization			X ¹							
GRF6019/Placebo Infusion			X	X	X	X	X			
Labs										
Screening Lab Panel ^c	X									
Urinalysis ^d	X				X ¹			X		X
ApoE Genotype Testing			X ¹							
Proteomics/epigenetics/biobanking			X ¹					X		X
Pre-infusion Safety Labs ^e				X ¹	X ¹	X ¹				
Follow-up Safety Labs ^f								X	X	
Exit Lab Panel ^g										X
Cognitive and Functional Assessments										
MMSE	X							X		X
Severe Impairment Battery		X						X	X	X
ADCS-ADL-severe		X								X
ADCS-CGIC		X						X	X	X
NPI or NPI-NH ^h		X						X		X

Notes:	X ¹ : To be performed prior to infusion start. During, and for 2 hours after, each infusion, vital signs should be collected according to the schedule outlined in the Infusion Administration Manual.
	a: Screening visit may be split to allow for sufficient time to complete all procedures. AEs and concomitant medications should be recorded during split visits, if applicable.
	b: The treatment window is 5 days. Visit 8 may occur on Day 6 + 1 to 3 days following treatment to potentially avoid a weekend visit, if needed. The preference for Visit 8 is for the subject to be seen on Day 6.

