2 GENERAL ANALYSIS DEFINITIONS

All analysis dataset preparations and statistical analyses will be performed using SAS® version 9.4 or higher. No imputation will be performed for missing data unless stated otherwise. Listings for CSR Appendix 16.2 will include all the subject data points being collected or derived for analyses, and will be sorted by treatment group, site, and subject number.

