2.3 Study Phase, Visit, and Day

The study is set up as shown above, along with study phase, visit, and day. In general, the baseline is defined as the last assessment before the first intake of the study medication unless otherwise specified. All scheduled assessments after first administration of study drug will be used.

Repeat/unscheduled assessments will not be used in descriptive statistics or any per-time point analyses but will be shown in listings as applicable. Pre-dose unscheduled assessments will be taken into account for baseline determination and post first dose unscheduled assessments will be taken into account for worst-case determination as applicable.

Reference date refers to the start date of the first study drug administration. All efficacy and safety assessments at all visits will be assigned a day relative to this date. The relative day will be defined as: visit date – reference date + 1 for visits on or after the reference date and visit date – reference date for visits before the reference date. Consequently, there is no 'Day 0' defined.

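### The Schedule of Events puts the mid-study NPI/NPI-NH at Visit 8 (Day 6), but protocol 7.3.5 and SAP 5.5 put it at Visit 9 (Day 12), so a site following the table would contribute nothing to the Day 12 summary

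*SAP*

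**What the plan says.** Three places fix the timing of the NPI or NPI-NH.

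- **SAP 5.5.** Change in "NPI or NPI-NH total severity score and total distress score will be calculated and summarized at each scheduled timepoint (Days 12 and 33"). No Day 6 summary is planned. The output is Table 14.2.5, on the Evaluable and Per Protocol sets.
- **Protocol 7.3.5.** The list under "Follow-up Visit 8 (Day 6 + 3 days") contains SIB and ADCS-CGIC only. The list under "Follow-up Visit 9 (Day 12 ± 3 days") contains SIB, ADCS-CGIC and, third, NPI or NPI-NH.
- **Protocol 15.1.** The row reads "NPI or NPI-NH ^h X X X", three marks in all. The SIB row just above reads "Severe Impairment Battery X X X X", four marks.

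Two general SAP rules decide what happens to a score taken on the other day. Section 2 states "No imputation will be performed for missing data unless stated otherwise". Section 2.3 states "Repeat/unscheduled assessments will not be used in descriptive statistics or any per-time point analyses but will be shown in listings as applicable".

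**The concern.** The two protocol sections name different visits for the same assessment, and the SAP can match only one of them. NPI has just two planned post-baseline time points, and the conflict is over one of them. A site that schedules from the table collects NPI at Visit 8, where the SAP has no column, and does not collect it at Visit 9, where the SAP has one. A site that schedules from 7.3.5 does the opposite. A Day 12 score that was never taken cannot be recovered later, and the SAP does not impute it.

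The two days are also not interchangeable. Protocol 4.1 has community-dwelling subjects admitted to a care facility for the dosing days, and protocol 7.1.1.3.5 requires an informant with daily contact. A Day 6 rating comes straight after that stay; a Day 12 rating comes nominally six days later.

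**Working it through.** No power or sample-size figure is involved. The check is a comparison of sources, followed by simple counts.

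**Step 1: column positions in 15.1.** Counting cells, including blanks, in the table as read from the PDF text gives:

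- NPI or NPI-NH: Visits 2, 8, 10
- SIB: Visits 2, 8, 9, 10
- ADCS-CGIC: Visits 2, 8, 9, 10
- ADCS-ADL-Severe: Visits 2, 10

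The SIB and ADCS-CGIC rows show where the Visit 8 and Visit 9 columns lie. Those rows, and the ADCS-ADL-Severe, ECG, targeted-exam, pre-infusion laboratory, follow-up laboratory and proteomics rows, all fall on the visits given in the text of 7.3. A column shift confined to the NPI row is therefore possible but not the likelier reading.

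**Step 2: the three sources side by side.**

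| Visit (nominal day) | Protocol 15.1 | Protocol 7.3 | SAP 5.5 |
|---|---|---|---|
| 2 (baseline) | NPI | NPI | baseline value |
| 8 (Day 6) | NPI | none | no column |
| 9 (Day 12) | none | NPI | column |
| 10 (Day 33) | NPI | NPI | column |

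The conflict is confined to Visits 8 and 9.

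**Step 3: the windows.** Visit 8 is Day 6 to Day 6 + 3 = Day 9. Visit 9 is Day 12 − 3 = Day 9 to Day 12 + 3 = Day 15. The nominal gap is 12 − 6 = 6 days. The possible gap runs from 0 (both on Day 9) to 15 − 6 = 9 days. The windows share one day only, and the SAP has no windowing rule that would move a Visit 8 score into the Day 12 column.

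**Step 4: how many subjects.** The plan expects 20 × (1 − 0.20) = 16 evaluable subjects, from "conducted at up to four (4) sites in the United States". The documents do not say which source a site uses, so the loss at Day 12 ranges from 0 to about 16. If four sites are of equal size (an assumption) and one follows the table, the loss is 16 / 4 = 4 subjects, or 25% of the summary. At 2:1 the 16 split as 16 × 2/3 = 10.7 and 16 × 1/3 = 5.3, so about 11 and 5. Randomization is stratified by sex and not by site, so one site's loss need not fall across the arms in that ratio.

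**Step 5: does anything settle the conflict?** Protocol 7.1.1.3 sends the reader to 7.3 for the timing of the scales, but 7.3.8, inside that same section, offers Section 15 as the summary of all procedures by visit. No precedence rule is stated. The revision history records NPI being added to 7.3.5 and 15.1 in version 2.0 and other edits to 15.1 in version 3.0, with no note on this difference. SAP section 8 does not mention it.

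**The case against.** The strongest reply is that the reading depends on counting blank cells in a table that did not survive extraction intact. The vital signs, weight, concomitant medication and adverse event rows are visibly cut short. The urinalysis row falls at Visit 5 where 7.3.4 says Visit 6. This stands as a reason to check the original PDF before anything is changed. It does not remove the point, because the rows nearest to NPI line up with the text.

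It can also be said that SAP 5.5 needs no correction, since it agrees with 7.3.5. That is right: the inconsistency lies inside the protocol, and the SAP is where its effect shows. Nor is the endpoint central. It is secondary, descriptive and unpowered, and any Visit 8 scores would still appear in Listing 16.2.6.5.

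Four stronger readings are tempting, and the documents do not support them.

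- *The Day 12 column will be empty.* That holds only if every site follows the table. Nothing shows how sites or the eCRF implemented the visit.
- *Behaviour would go unmeasured at Day 12.* ADCS-CGIC also covers behaviour and is summarized at Days 6, 12 and 33. NPI is the only dedicated behavioural scale.
- *A quarter of 20 subjects, so 5, would be lost.* Table 14.2.5 uses the Evaluable and Per Protocol sets, for which the planning figure is about 16, and equal site sizes are an assumption.
- *The table is simply the wrong source.* For MMSE the pattern is reversed: 15.1 and SAP 5.1 place it at Visit 8 (Day 6), and 7.3.5 omits it there. Neither protocol section is consistently the one that the SAP follows.

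**Conclusion.** The inconsistency is real as printed. Protocol 15.1 gives NPI at Visits 2, 8 and 10; protocol 7.3 and SAP 5.5 give Visits 2, 9 and 10. One of the two post-baseline NPI time points is exposed. The number missing from the Day 12 summary lies between none and all of about 16 subjects; about 4 is an illustration that assumes four equal sites with one following the table. The 16 is a planning figure tied to five doses and completion of Visit 8, whereas the Evaluable set requires only four doses, so the actual denominator may differ somewhat.

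The effect is on the completeness and day-consistency of Table 14.2.5. It does not reach baseline NPI, Day 33 NPI, the sample size or the primary safety endpoint. The conclusion rests on the extracted table matching the original, which should be confirmed.

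**What to change.** 1. Check the NPI row of 15.1 against the original PDF.
2. If the row is as read here, reconcile 15.1 with 7.3.5 and SAP 5.5. Two of the three sources already give Visits 2, 9 and 10. Settle the MMSE mismatch at Visit 8 in the same correction, since it also comes from 15.1 and 7.3.5 disagreeing.
3. Tell sites by clarification memo. The sponsor has already used this route for an omission in the same table (HbA1c).
4. Add one sentence to SAP 5.5: NPI scores already collected at Visit 8 are shown in Table 14.2.5 under a separate Day 6 column, with their own count, and are not pooled with Day 12.

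For NPI, the cost is one table row, one memo and one SAP sentence, with the MMSE entry settled in the same memo. Aligning the NPI row with 7.3.5 and the SAP adds no visit and no procedure.

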6 SAFETY

All safety analyses will be done on the Safety Set.

6.1 Adverse Events

6.1.1 Coding of AEs

The verbatim terms of AEs will be coded using the Medical Dictionary for Regulatory Activities (MedDRA). Events are looked at on the level of their preferred term and system organ class.

6.1.2 Treatment-Emergent AE

Pre-treatment AEs are defined as AEs that were reported or worsened after signing the ICF up to the start of study drug dosing. Treatment-emergent AEs (TEAE) are defined as AEs that were reported or worsened on or after the start of study drug dosing and up to and including the end of the follow-up.

6.1.3 Variables Attributed to Adverse Events:

- AE term (verbatim and MedDRA preferred term and system organ class)
- Onset datetime, End datetime, Study Day and duration of AE
- Serious AE (Yes/No), if yes classification will be listed (Death, Life-threatening Disability or Permanent Damage, Hospitalization – initial or prolonged, Congenital Anomaly/Birth Defects, Other Serious (Important Medical Events)).
- AE of special interest
- Frequency (Single Episode, Intermittent, Continuous)
- Severity (Mild, Moderate, Severe)
- Relation to study treatment (Unrelated, Possibly Related, Definitely Related)
- Action taken with study treatment (No Action Taken, Treatment Held, Treatment Discontinued)
- Other Action due to AE (No Action, Medication Therapy, Non-Drug Therapy, Other)
- Outcome of AE (Recovered/Resolved, Not Recovered/Not Resolved, Recovered/Resolved with Sequelae, Fatal, Unknown)
- AE leading to death (Yes/No)

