4.2 STUDY ENDPOINTS

4.2.1 PRIMARY ENDPOINTS

The primary endpoints pertain to safety and tolerability of the GRF6019 dosing regimen in subjects with severe AD.

The primary safety endpoint is as follows:

- Incidence of treatment-emergent adverse events (AEs) and serious adverse events (SAEs) identified by MedDRA PT and grouped by MedDRA SOC.

Tolerability endpoint is as follows:

- Number of subjects completing 4 weeks after receiving at least 5 infusions.

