8.1 SPECIFICATION OF SAFETY PARAMETERS

8.1.1 DEFINITION OF ADVERSE EVENTS (AE)

Per 21 CFR 312.32(a) an AE is any untoward (unfavorable, harmful, or pathologic) medical occurrence in a subject administered a medicinal (investigational) product even if the event does not necessarily have a causal relationship with this treatment.

An AE can therefore be any unfavorable and unintended sign (including an abnormal laboratory finding that is deemed clinically significant), symptom, or disease temporally associated with the use of a medicinal

(investigational) product whether or not related to the medicinal (investigational) product.

An AE does include any:

- Exacerbation of a pre-existing illness.
- Subjective or objective symptoms spontaneously offered by the subject or the subject's caregiver and/or observed by the investigator or study staff.
- Increase in frequency or intensity of a pre-existing episodic event or condition.
- Condition detected or diagnosed after study drug administration even though it may have been present prior to the start of the study (unless it can be demonstrated by medical record review that the onset of the event preceded the date/time of Informed Consent).
- Continuous persistent disease or symptoms present at baseline that worsen following the start of the study.
- Symptoms associated with disease not previously reported by the subject/caregiver.
- Untoward medical occurrences considered by the investigator to be related to study-mandated procedures.
- Abnormal assessments (e.g., change on physical examination, ECG findings), if they represent a clinically significant finding, that were not present at baseline or worsened during the course of the study.
- Laboratory test abnormalities, if they represent a clinically significant finding, symptomatic or not, which were not present at baseline or worsened during the course of the study.

An AE DOES NOT include a/an:

- Elective medical or surgical procedure (e.g., surgery, endoscopy, tooth extraction, transfusion).
- Pre-existing diseases or conditions present or detected at the start of the study that do not worsen.
- Situations where an untoward medical occurrence has not occurred (e.g., hospitalization for cosmetic elective surgery, social and/or convenience admissions).
- The disease or disorder being studied or sign or symptom associated with the disease or disorder unless more severe than expected for the subject's condition.

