8.4 REPORTING PROCEDURES

8.4.1 ADVERSE EVENT REPORTING

All subjects who have given informed consent will be evaluated for AEs. All AEs that occur after the time of treatment with the study agent will be considered Treatment Emergent AEs. Subjects with Treatment-Emergent AEs must be followed until the AE is resolved or is stable, unless the subject is lost to follow up.

Each AE or suspected adverse reaction must be described as follows: the date of onset, date of resolution, severity (mild, moderate, severe), frequency of the event (single episode, intermittent, continuous), action taken with study treatment (no action taken, treatment held, treatment discontinued), outcome, causality* (unrelated, possibly related, definitely related), and seriousness criteria. Each AE or suspected adverse reaction must be recorded separately.

***Note:** Causality assessment will be made only when the AE occurs after the subject has initiated at least one infusion of the study agent. An AE occurring before the subject's exposure to study agent will always be labeled as "unrelated".

Any AE occurring during the study must be documented in the subject's medical records and as an AE in the CRF. Any SAE occurring during the study must be documented in the subject's medical records and as an SAE in the CRF.

A separate set of SAE pages should be used for each SAE. However, if at the time of initial reporting,

multiple SAEs are present that are temporally and/or clinically related, they may be reported on the same SAE page.

The investigator should attempt to establish a diagnosis of the event (that meets the definition of an AE or SAE) based on signs, symptoms, and/or other clinical information. In such cases, the diagnosis should be documented as the AE and/or SAE and not the individual signs or symptoms. The diagnosis will become the basis for the verbatim term as reported by the investigator. If no diagnosis is known, and clinical signs and symptoms are not present, the abnormal finding should be recorded.

In addition to the investigator's own description of the AEs, each AE will be encoded according to the MedDRA.

The investigator will take all appropriate and necessary therapeutic measures required for resolution of the AE. Any medication necessary for the treatment of an AE must be recorded on the concomitant medication CRF.

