10.4.2 ANALYSIS OF THE PRIMARY ENDPOINT

Safety and tolerability will be evaluated by examining the occurrence of AEs, including Treatment-Emergent AEs and AEs leading to discontinuation from the study.

Summary tabulations of reported AEs will be presented by group after the Verbatim Terms have been coded to PTs and SOCs using the MedDRA Version 21.0 coding dictionary. The summaries will include severity and attribution to the study agent. Multiple reports of the same AE by the same subject will be counted only once at the highest severity and strongest attribution to the study agent.

The AE analyses will focus on those that are treatment-emergent, however any AEs that are reported after consent has been signed and prior to initial dosing will be tabulated as Intercurrent Events.

Additional details are presented in [Section 10.4.4](#).

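### The SAP classes adverse events as treatment-emergent by when they were reported or worsened, the protocol by when they occurred, and the difference is neither recorded nor resolved

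*SAP*

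**What the plan says.** The primary safety endpoint in protocol 4.2.1 is "Incidence of treatment-emergent adverse events (AEs) and serious adverse events (SAEs) identified by MedDRA PT and grouped by MedDRA SOC". Three places say which events belong to the treatment period.

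- **SAP 6.1.2.** TEAEs are "defined as AEs that were reported or worsened on or after the start of study drug dosing", through the end of follow-up. The companion class uses the same test: "Pre-treatment AEs are defined as AEs that were reported or worsened after signing the ICF up to the start of study drug dosing".
- **Protocol 8.4.1.** "All AEs that occur after the time of treatment with the study agent will be considered Treatment Emergent AEs". The same section has every event that occurs before exposure labelled as unrelated to the study agent.
- **Protocol 10.4.2.** On events before dosing: "any AEs that are reported after consent has been signed and prior to initial dosing will be tabulated as Intercurrent Events".

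SAP 6.1.3 lists the AE timing variables as "Onset datetime, End datetime, Study Day and duration of AE". It lists no report date. SAP 8 records two changes from the protocol, the Per Protocol dataset and the blood pressure ranges, and is silent on the TEAE definition.

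**The concern.** Onset appears in neither SAP definition. The worsening limb is proper and should stay. The difficulty is the word *reported*: it lets the date on which someone mentioned an event decide whether the event belongs to the treatment period. Protocol 8.4.1 uses a different test, and protocol 10.4.2 uses the reporting test again, so the protocol does not settle which is meant.

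At stake is the numerator of the primary safety endpoint. An event cannot be reported before it begins, so replacing onset with report date can move events only one way, into the TEAE count. Such events are foreseeable under the protocol. Section 8.1.1 counts as an AE any "Condition detected or diagnosed after study drug administration even though it may have been present prior to the start of the study", unless records show onset before consent. Subjects have MMSE scores of 0 to 10, and AE information comes partly from caregivers.

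**Working it through.** The plan states no figure on this point, so the check is mainly a comparison of texts.

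**Step 1. Run each kind of event through the three rules.**

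| Onset | First reported | Worsened after first infusion | SAP 6.1.2, literal | Protocol 8.4.1 | Protocol 10.4.2 |
|---|---|---|---|---|---|
| Before | Before | No | Pre-treatment | Not a TEAE | Intercurrent Event |
| Before | After | No | **TEAE** | **Not a TEAE** | **Not an Intercurrent Event** |
| Before | Before | Yes | Pre-treatment, then TEAE on worsening | No explicit worsening limb; 8.1.1 treats worsening as an AE | Intercurrent Event for the initial report |
| After | After | Not applicable | TEAE | TEAE | Not an Intercurrent Event |

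The second row is the problem. The SAP counts the event as a TEAE. Under the protocol it fits neither class. Because it began before exposure, protocol 8.4.1 has it labelled unrelated, so in the SAP tables it would appear as an unrelated TEAE.

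**Step 2. Weight of one such event.** Inputs: about 20 subjects randomized 2:1 (protocol 10.5, SAP 1.3), so 20 × 2/3 ≈ 13 active and 20 × 1/3 ≈ 7 placebo. One subject is worth 100/n percentage points:

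- active: 100/13 = 7.7 points
- placebo: 100/7 = 14.3 points
- with a 14/6 split: 100/14 = 7.1 and 100/6 = 16.7 points

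The shift applies to the any-TEAE row only if the subject has no other TEAE. It applies to a preferred-term row whenever the subject has no other event with that term.

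**Step 3. How often?** The documents give no rate. Let q be the assumed share of subjects with a late-reported pre-dose event. The expected number among 20 is 20q, and the chance of at least one is 1 − (1 − q)^20.

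| q (assumed) | Expected number | Chance of at least one |
|---|---|---|
| 2% | 0.4 | 33% |
| 5% | 1.0 | 64% |
| 10% | 2.0 | 88% |

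**Step 4. Effect on the comparison.** If such events arise equally in both arms and independently of true TEAEs, the observed incidence is 1 − (1 − p)(1 − q), where p is the true incidence. The difference between arms is therefore multiplied by (1 − q). Assuming true incidences of 70% and 50% with q = 5%, the observed values are 71.5% and 52.5%, a difference of 19.0 points instead of 20. Both arms rise and the contrast shrinks slightly.

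**The case against.** The strongest reply is that *reported* is loose drafting for *began*. SAP 6.1.3 lists onset datetime and no report date, so a programmer would most naturally use onset. SAP 6.1.4 sorts blood pressure events by start date. SAP 1 says the SAP is to be read together with the protocol. This is plausible, and a reader should not conclude that the analysis will certainly be run on report date. It does not dispose of the point, because the protocol itself uses *reported* for pre-dose events in 10.4.2. For the same reason, the SAP should not be described as departing from a protocol that is consistent on this matter.

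Other parts of the reply stand and limit the consequence:

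- AEs are reviewed at Baseline and again before the Visit 3 infusion. A late-recalled event must have been missed at every review after its onset. Severe dementia and reliance on caregivers make late recall possible, but the documents do not show that it is likely.
- Assessors are blinded, the rule is identical in both arms, and SAP 6.1.4 plans no formal testing unless otherwise indicated. A reader might infer that the active arm is inflated relative to placebo. The documents do not support that; at about 13 against 7, only chance imbalance could produce it.
- The error over-counts events and does not hide them. Events that began before exposure are labelled unrelated, so drug-related counts should not change. Listings 16.2.7.1 and 16.2.7.2 cover non-emergent and emergent events, so with onset recorded a misplaced event should be visible.

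**Conclusion.** The conflict is real and should be resolved before database lock, but it is modest. SAP 6.1.2 and protocol 8.4.1 give different answers for one kind of event, protocol 10.4.2 does not settle the matter, and SAP 8 does not record it. The primary safety endpoint therefore has two defensible readings.

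The only size that needs no assumed event rate is the weight of one subject: about 7.7 points in the active arm or 14.3 points in the placebo arm. This assumes a Safety Dataset of about 13 and 7, and a subject with no other event in the row concerned.

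A reader might go further and derive a percentage of affected subjects from assumed inputs. For example, take 0.01 to 0.03 AEs per subject-day, 5% to 20% of them reported late, and 8 to 28 pre-dose days. Then 1 − exp(−rate × share × days) runs from 0.4% to 15.5%. That span of almost 40-fold reflects the assumptions alone, and its upper end ignores the AE reviews before dosing. It should not be quoted as an estimate for this trial.

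**What to change.** 1. In SAP 6.1.2, define a TEAE as an AE with onset datetime at or after the start of the first infusion, or a pre-existing AE that worsens after that time, through the end of follow-up.
2. Define pre-treatment AEs by onset or worsening after consent and before the start of the first infusion.
3. State how missing or partial onset dates and times are classified, including Day 1 events with no time. SAP 2 rules out imputation unless stated otherwise, so an onset rule cannot place these events without such a statement. One option is to count them as treatment-emergent unless the available part of the date or time shows onset before the first infusion.
4. Align the Intercurrent Events wording in protocol 10.4.2 with the occurrence wording in 8.4.1.
5. Record the change in SAP 8.

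The cost is a few sentences across the two documents. Onset datetime is already a listed AE variable, so no new data are needed.
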